14.2. Assessment and Recording of Adverse Events

The SI will carefully monitor each subject throughout the study for possible AEs. All AEs will be documented on CRFs designed specifically for this purpose. All AEs will be collected and reported in the EDC system and compiled into reports for monthly reviewing by the Medical Monitor. The Medical Monitor shall promptly review all information relevant to the safety of the investigational product, including all SAEs. Special attention will be paid to those that result in permanent discontinuation of the investigational product being studied, whether serious or non-serious.

14.2.1. Assessment of Adverse Events

At each visit (including telephone interviews), the subject will be asked if they have had any problems or symptoms since their last visit in order to determine the occurrence of AEs. If the subject reports an AE, the SI will probe further to determine:

1. Type of event
2. Date of onset and resolution (duration)
3. Severity (mild, moderate, severe)
4. Seriousness (does the event meet the above definition for an SAE)
5. Causality, relation to investigational product and disease
6. Action taken regarding investigational product
7. Outcome

14.2.2. Relatedness of Adverse Event to Investigational Product

The relationship of the AE to the investigational product should be specified by the SI using the following definitions:

1. Not Related: Concomitant illness, accident or event with no reasonable association with treatment.
2. Unlikely: The reaction has little or no temporal sequence from administration of the investigational product, or a more likely alternative etiology exists.
3. Possibly Related: The reaction follows a reasonably temporal sequence from administration of the investigational product and follows a known response pattern to the suspected investigational product; the

reaction could have been produced by the investigational product or could have been produced by the subject's clinical state or by other modes of therapy administered to the subject. (Suspected ADR)

4. Probably Related: The reaction follows a reasonably temporal sequence from administration of investigational product; is confirmed by discontinuation of the investigational product or by re-challenge; and cannot be reasonably explained by the known characteristics of the subject's clinical state. (Suspected ADR)

5. Definitely Related: The reaction follows a reasonable temporal sequence from administration of investigational product; that follows a known or expected response pattern to the investigational product; and that is confirmed by improvement on stopping or reducing the dosage of the investigational product, and reappearance of the reaction on repeated exposure (Suspected ADR).

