14.1. Definitions of AEs, Suspected Adverse Drug Reactions & SAEs

14.1.1. Adverse Event and Suspected Adverse Drug Reactions

An AE is any unfavorable and unintended sign (including a clinically significant abnormal laboratory finding, for example), symptom, or disease temporally associated with a study, use of a drug product or device whether or not considered related to the drug product or device.

Adverse drug reactions (ADR) are all noxious and unintended responses to a medicinal product related to any dose. The phrase “responses to a medicinal product” means that a causal relationship between a medicinal product and an AE is at least a reasonable possibility, i.e., the relationship cannot be ruled out. Therefore, a subset of AEs can be classified as suspected ADRs, if there is a causal relationship to the medicinal product.

Examples of AEs include: new conditions, worsening of pre-existing conditions, clinically significant abnormal physical examination signs (e.g., skin rash, peripheral edema), or clinically significant abnormal test results (e.g., lab values or vital signs), with the exception of outcome measure results, which are not being recorded as AEs in this trial (they are being collected, but analyzed separately). Stable chronic conditions (e.g., diabetes, arthritis) that are present prior to the start of the study and do not worsen during the trial are NOT considered AEs. Chronic conditions that occur more frequently (for intermittent conditions) or with greater severity, would be considered as worsened and therefore would be recorded as AEs.

AEs are generally detected in two ways:

Clinical → symptoms reported by the subject or signs detected on examination.

Ancillary Tests → abnormalities of vital signs, laboratory tests, and other diagnostic procedures (other than the outcome measures, the results of which are not being captured as AEs).

For the purposes of this study, symptoms of progression/worsening of ALS, including ‘normal’ progression, will be recorded as AEs.

The following measures of disease progression will not be recorded as AEs even if they worsen (they are being recorded and analyzed separately): vital capacity results and ALSFRS-R results.

If discernible at the time of completing the AE log, a specific disease or syndrome rather than individual associated signs and symptoms should be identified by the SI and recorded on the AE

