log. However, if an observed or reported sign, symptom, or clinically significant laboratory anomaly is not considered by the SI to be a component of a specific disease or syndrome, then it should be recorded as a separate AE on the AE log. Clinically significant laboratory abnormalities, such as those that require intervention, are those that are identified as such by the SI.

Subjects will be monitored for AEs from the time they sign consent until completion of their participation in the study (defined as death, consent withdrawal, loss to follow up, early study termination for other reasons or following completion of the entire study).

An unexpected AE is any AE, the specificity or severity of which is not consistent with the current IB. An unexpected, suspected ADR is any unexpected AE that, in the opinion of the SI or Sponsor, there is a reasonable possibility that the investigational product caused the event.

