3.2.3 Safety Endpoints

The following safety endpoints will be evaluated:

- Proportion of participants experiencing and number of unique events of each type of TEAE and serious TEAE classified by MedDRA system organ class and preferred term,
- Proportion of participants experiencing and number of unique events of TEAEs classified by seriousness, severity, relatedness to study drug, relatedness to TMS and TTNCS procedures, action taken with study drug, action taken with TMS/TTNCS, and outcome, summarized across all MedDRA terms,
- Instances of treatment-emergent and clinically significant laboratory abnormalities classified by assay, whether the abnormality is below or above the normal range,
- Mean change from baseline in weight
- Proportion of participants experiencing treatment-emergent and clinically significant ECG abnormalities by type of finding
- Proportion of participants experiencing treatment-emergent and clinically significant physical examination findings by body system
- Proportion of participants experiencing treatment-emergent neurological examination findings by type of finding

Reported proportions will use as their denominator all participants in the Safety and Tolerability sample (see Section 3.5 below).

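### The relatedness scale in Protocol 14.2.2 has no suspected-ADR level for a new type of event without dechallenge or re-challenge, although 14.1.1 would make that event a suspected ADR

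*Protocol*

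**What the plan says.** Protocol 14.1.1 sets the general test. An event counts as a suspected ADR when a "causal relationship between a medicinal product and an AE is at least a reasonable possibility, i.e., the relationship cannot be ruled out". The same section makes clear that novelty is no bar: "An unexpected, suspected ADR is any unexpected AE that, in the opinion of the SI or Sponsor, there is a reasonable possibility" that the product caused it.

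Protocol 14.2.2 gives the working instrument. The relationship of each event to the product "should be specified by the SI using the following definitions". There are five levels, and only levels 3, 4 and 5 carry the suspected-ADR mark:

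- Level 1, Not Related: "Concomitant illness, accident or event with no reasonable association with treatment".
- Level 2, Unlikely: "The reaction has little or no temporal sequence from administration of the investigational product, or a more likely alternative etiology exists".
- Level 3, Possibly Related: reasonable timing, and the reaction "follows a known response pattern to the suspected investigational product". A further clause says that the product, the clinical state or another therapy could have produced it.
- Level 4, Probably Related: reasonable timing, the reaction "is confirmed by discontinuation of the investigational product or by re-challenge", and the clinical state gives no reasonable explanation.
- Level 5, Definitely Related: a known or expected pattern, improvement when the drug is stopped or reduced, and recurrence on repeated exposure.

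Protocol 14.2.3 makes the relationship a required entry, due within 48 hours of the site learning of the event or of an update to it. SAP 3.2.3 then reports "TEAEs classified by seriousness, severity, relatedness to study drug" and other attributes. SAP 3.8.1 counts participants by the worst level each experienced and treats an unknown value as not the worst. The SAP defines no relatedness scale of its own and refers to the protocol for adverse event definitions.

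**The concern.** One term, suspected ADR, has two tests in the same chapter. The general definition asks whether causality is reasonably possible. The scale the investigator fills in asks, at its lowest qualifying level, whether the reaction is already known for the drug. The levels above it do not take in everything that this condition excludes.

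The investigator's label is the relatedness record that is collected and tabulated. If the scale cannot express that a new reaction might be due to the drug, such an event must either be given a level whose definition it does not meet or be left without a level. In both cases it is missing from the suspected-ADR levels of the relatedness summaries. The event is still recorded; what is lost is its correct label.

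**Working it through.** No power or alpha calculation applies. The check is whether one kind of event satisfies any of the five definitions, read as logical conditions, and then what 14.1.1 says about the same event.

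**Test case.** The event is of a type not known for mexiletine. Its timing is plausible, no other cause is more likely, and there is no dechallenge or re-challenge information. That last condition arises when the event is fatal or irreversible, resolves while the drug continues, or is assessed before the drug is stopped.

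| Level in 14.2.2 | Condition that decides | Met? |
|---|---|---|
| 1 Not Related | no reasonable association | No: the timing fits and nothing else explains it better |
| 2 Unlikely | poor timing, or a likelier cause | No: neither applies |
| 3 Possibly (suspected ADR) | timing and known pattern | No: the pattern is not known |
| 4 Probably (suspected ADR) | confirmed by stopping or re-challenge | No: no such information |
| 5 Definitely (suspected ADR) | known or expected pattern, improvement, recurrence | No: none is available |

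No level fits, and all three suspected-ADR levels are closed.

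**Is level 3 really conjunctive?** Yes. The timing and pattern conditions are joined by *and*. The clause after the semicolon, on possible producers of the reaction, is a further statement and not an alternative route into the level.

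**The same event under 14.1.1.** Causality cannot be ruled out, so it is a suspected ADR. Because its type is new, it is an unexpected one. The two sections give opposite answers.

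**Edge of the gap.** A new type of event that does resolve on stopping can reach level 4, which has no known-pattern condition. It still misses level 4 if the clinical state could reasonably explain it, even where that is not the likelier cause.

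**After the change proposed below.** With level 3 defined by plausible timing and a reasonable possibility of causation, the test case meets level 3 and is a suspected ADR under both sections. Levels 4 and 5 need no edit for this to hold.

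**The case against.** The strongest reply is that little depends on this label and few events are affected. Much of that stands.

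- **Other routes exist.** Protocol 14.1.1 and 14.1.2 rest unexpected and serious suspected ADRs on the opinion of the investigator or the sponsor, without citing the scale, so the sponsor can still call such an event a suspected ADR. This is correct, but the investigator's prescribed scale has no level for that opinion.
- **The design supplies some dechallenge.** All participants stop drug by Week 4 and are seen at Week 8, and 6.4 follows events to resolution or for 28+5 days after stopping. A reversible reaction still present at Week 4 may later reach level 4. This narrows the gap but does not help the cases listed in the working.
- **The known pattern is broad.** Protocol 2.2.3 lists reactions across many organ systems, so events of a truly new type should be few.

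A reader might also infer more than the documents support:

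- *That every unexpected event, or every death, without dechallenge is shut out.* Under 14.1.1 an event may be unexpected only in severity and still follow a known pattern. A death from a recognised type of reaction can also meet level 3.
- *That such events must be recorded as Not Related.* They do not meet that definition either; the correct finding is that no level fits.
- *That dose selection is distorted.* Protocol 13.8 relies on rates of AEs, SAEs, mortality, clinical abnormalities and early termination or withdrawal. It does not mention relatedness.
- *That the safety detection figure in 13.7 is undermined.* With 40 exposed participants and a 4% event, 1 − 0.96^40 = 0.805, which matches the stated 80%. That is the chance of observing any safety outcome, whatever its relatedness label.
- *That serious events go unreported or stopping is affected.* Protocol 14.2.3 and 14.3 require 24-hour SAE reporting with no relatedness condition. Section 6.4 speaks of drug-related events but does not cite the scale.
- *That this is a first look at an unknown drug.* Protocol 2.2.3 describes controlled studies at 600 to 1200 mg/day and more than 10,000 compassionate-use patients. Protocol 2.1.3.2 describes an ALS trial at 300 and 900 mg/day.

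**Conclusion.** The contradiction between Protocol 14.1.1 and 14.2.2 is real and should be reconciled. Its reach is narrow: events new in type, with plausible timing, no likelier cause and no dechallenge or re-challenge. For that class the scale offers no fitting level and no way for the investigator to record a suspected ADR.

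Three things are affected: the investigator's relatedness label, the recognition of unexpected suspected ADRs through that label, and the relatedness summaries in SAP 3.2.3 and 3.8.1. AE capture, SAE reporting, counts by MedDRA term, the stated dose-selection criteria and the primary endpoint are not affected.

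The documents give no rate for such events, so the number of labels changed cannot be estimated. The conclusion assumes that investigators apply the five definitions as written. Investigators who rely on the general definition in 14.1.1 may choose Possibly Related anyway, and the labels would then vary between sites.

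**What to change.** In Protocol 14.2.2, define Possibly Related as a reasonable time sequence with the product as a reasonable possible cause, using the test already in 14.1.1. Delete the condition that the reaction "follows a known response pattern to the suspected investigational product". Carry the same wording into the CRF completion guidance. Levels 4 and 5 can stay as they are, since the change to level 3 alone removes the contradiction.

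The cost is a protocol wording change and updated site guidance. No endpoint, sample size, visit or analysis changes. The downside is that a few more events will be classed as suspected ADRs, which 14.1.1 already intends.

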14.2.3. Recording of Adverse Events

All clinical AEs are recorded in the AE Log in the subject's study binder. The site should fill out the AE Log and enter the AE information into the EDC system within 48 hours of the site learning of a new AE or receiving an update on an existing AE.

Please Note: SAEs must be reported to the NCRI CC within 24 hours of the site learning of the SAE. This applies regardless of whether the subject is taking study drug or not. Any events of drug-induced liver injury whether classified as SAEs or not, must also be reported within 24 hours.

Entries on the AE Log (and into the EDC) will include the following: name and severity of the event, the date of onset, the date of resolution, relationship to investigational product, action taken, and primary outcome of event.

14.3 Adverse Events and Serious Adverse Events - Reportable Events

The following are considered reportable events and must be reported to the NCRI CC within 24 hours of the site being notified of the event.

- All events that meet the above criteria for Serious Adverse Events (SAEs)
- Dosage Changes (Dose Management)
 - Investigational Product Suspension, Reduction or Re-challenge
 - Investigational Product Discontinuation
- Key Study Events:
 - Subject Final Disposition
 - Feeding Tube Placement
 - Permanent Assisted Ventilation (PAV)*
 - Tracheostomy

- Mortality
- Pregnancy
- Diaphragm Pacing System (DPS) device implantation

* Permanent Assisted Ventilation (PAV) is defined as more than 22 hours daily of non-invasive mechanical ventilation for more than one week. The date of onset of PAV is the first day of the seven days.

15.0. DATA COLLECTION, MANAGEMENT AND MONITORING

15.1. Role of Data Management

Data Management is the development, execution and supervision of plans, policies, programs, and practices that control, protect, deliver, and enhance the value of data and information assets.

All data will be managed in compliance with NEALS policies, and applicable Sponsor and regulatory requirements. Site personnel will collect, transcribe, correct, and transmit the data onto source documents, Case Report Forms (CRFs), and other forms used to report, track and record clinical research data. Clinical sites will be monitored to ensure compliance with data management requirements and Good Clinical Practices. NCRI Data Management is responsible for developing, testing, and managing clinical data management activities.

15.1.1. Data Entry and Checks

The site personnel are instructed to enter information into the EDC System within 5 days of a visit. Data collection is the responsibility of the staff at the site under the supervision of the SI. During the study, the SI must maintain complete and accurate documentation for the study.

The EDC includes password protection. An edit checking and data clarification process will be put in place to ensure accuracy and completeness of the database. Logic and range checks as well as more sophisticated rules will be built into the EDC to provide immediate error checking of the data entered. The system has the capability to automatically create electronic queries for forms that contain data that are out of range, out of window, missing or not calculated correctly. The sites will only have access to the queries concerning their subjects.

15.1.2. Database Security

The MS SQL Server database is located on a secure database server. This server is located in a restricted area of the Partners Healthcare server farm and physical access to it is limited to authorized personnel only. Both database and Web servers are located on the Partners Healthcare network behind the firewall. Access to the data at the clinical site will be restricted and monitored through the system's software with its required log-on, security procedures and audit trail. The data will not be altered, browsed, queried, or reported via external software applications that do not enter through the protective system software. There will be a cumulative record that indicates, for any point in time, the names of authorized personnel, their titles, and a description of their access privileges. The record will be in the study documentation accessible at the site. Controls will be in place to prevent, detect, and mitigate effects of computer viruses on study data and software. The application utilizes SSL (Secure Sockets Layer) technology and 128-bit encryption to comply with requirements of 21 CFR Part 11 for Open Systems. Backups of the database will be performed nightly using the services provided by the MGH network. All PCs run virus protection software full-time and are updated with the latest virus detection strings regularly; the Windows NT server does this as well and has the additional security of scanning all e-mail for viruses before a user can even access them. All accounts are password protected and passwords must be changed on a regular basis.

In addition, the EDC system will have an extra level of password security. At study initiation, the Data Manager will set default passwords for the relevant study personnel at the study sites. When a new user logs in with the assigned username and default password for the first time, he or she will be forced to change the password to a unique one (at least six characters long), known only to the user. An ongoing paper log will be kept showing when usernames and passwords are set up, for whom, in what user capacity and when usernames are disabled. In case an employee forgets her/his password, they will submit a password request form via email to the Data Manager, who will issue a new default password. They must then go through the Change Password process. The passwords will expire every 90 days, users will then be required to go through the Change Password process. To avoid password-based software attacks, the system will lock a user for one minute if an incorrect password is provided three times in a row. A user will also be able to change the password at will if he or she feels that it may have been compromised.

15.1.3. Data Lock Process

The application will have the ability to lock the database to prevent any modification of data once the study is closed. Once this option is activated, every user will have Read-Only access to the data. The database can only be locked after each SI has signed off on their subjects and all queries have been resolved.

15.1.4. Quality Assurance

Protocol procedures are reviewed with the SI and associated personnel prior to the study to ensure the accuracy and reliability of data. Each SI must adhere to the protocol detailed in this document and agree that any changes to the protocol must be approved by the NCRI Coordination Center prior to seeking approval from the site IRB. Each SI will be responsible for enrolling only those study subjects who have met protocol eligibility criteria.

15.2. Study Monitoring

Study Monitors will visit each study site to review source documentation materials, ICFs, and confirm entered data and that data queries have been accurately completed, and again at a study close-out visit. Study Monitors will also verify that SAEs and protocol deviations have been reported appropriately, as required. The Study Monitors will also review clinical facilities, resources and procedures for evaluating study subjects and study drug dispensing. Subsequently, the Study Monitors will provide monitoring reports to the Project Manager and, if requested, will provide reports of protocol compliance to the Study PI and the Steering Committee. Completed ICFs from each subject must be available in the subject's file and verified for proper documentation. A document outlining the monitoring plan is provided to each Study Monitor.

